#### 4.2. Sample Size and Power

The sample size of 4 subjects in each of the single-dose cohorts (Cohorts 1 and 2) and 6 to 8 subjects in the 800 mg multiple-dose cohort will allow for the characterization of the central tendency of PK parameters as they relate to ALXN1210 and to gain initial knowledge of PK/PD relationships in Japanese subjects. To ensure future modeling and simulations are accurate, it is preferred to estimate the PK parameters with a maximum imprecision of < 25% following the IV administration of ALXN1210. Six subjects in Cohort 3 will provide 23.3%

maximum imprecision (Table 1) for the estimation of area under the serum concentration versus time curve from time 0 extrapolated to infinity (AUC $\infty$ ), in terms of the relative distance of the lower 90% confidence limit from the observed PK parameter that will be obtained with 80% assurance and assuming the within-subject SD of the log-transformed AUC $\infty$  is as much as 0.19.

Table 1:	Estimation of the Maximum Imprecision in the Estimate of PK	
	Parameters for Selected Sample Sizes	

Number of Subjects on Active	Maximum Imprecision (%)
4	33.6
6	23.3
8	18.9

### 4.3. Demographics, Baseline Characteristics, and Subject Disposition

All subjects will be included in the summary of subject disposition, which will summarize the frequency and percentage of subjects screened and treated who completed or discontinued from the study, along with reason for discontinuation, by treatment group. Demographics and baseline characteristics will be summarized for all subjects by each treatment dose and overall on the safety population. If the remaining populations are different from the safety population, separate demographic tables will be produced. Continuous variables will be summarized using n, arithmetic mean, standard deviation, median, minimum, and maximum whereas categorical variables will be summarized by frequency and percentage by treatment group.

## 4.4. Safety Analysis

Safety analyses will be performed on the safety population, and will be reported by each treatment dose. Safety analyses will include an analysis of all AEs, ECGs, clinical laboratory data, physical examinations, and vital sign measurements and will be presented using descriptive statistics. No inferential statistical analyses are planned on the safety parameters of this study.

#### Adverse Events

The incidence of treatment-emergent (after dosing) AEs (TEAEs) will be summarized using the safety population. The Medical Dictionary for Regulatory Activities (MedDRA®) dictionary Version 19.0 (or higher) will be used to classify all AEs reported during the study by System Organ Class (SOC) and preferred term (PT). A summary of adverse events including the incidence of subjects who experience TEAEs and incidence of TEAEs (number of events) will be presented for each treatment dose and overall, by severity and by relationship to study drug. SAEs will be summarized by system organ class and preferred term for each treatment dose and overall, by severity, and by relationship to study drug.

SAEs and AEs resulting in withdrawal from the study will be listed. Subjects having multiple AEs within a category (e.g., overall, system organ class and preferred term) will be counted once in that category. For severity tables, a subject's most severe event within a category will be counted. In each table,

SOC will be presented in descending order of overall incidence rate (alphabetical order will be used in case of equal rates).

#### Medical history

Medical history data will be coded using MedDRA  $\ensuremath{\mathbb{R}}$  dictionary Version 19.0 (or higher) and listed individually.

#### Study drug administration

Study drug administration data will be listed individually.

#### Vital signs

Vital signs data (systolic and diastolic blood pressure, heart rate, oral temperature, and respiration rate) will be listed for individual subjects. Summary statistics (n, arithmetic mean, SD, median, minimum, and maximum) of absolute values and changes from baseline will be calculated for each parameter by each treatment dose.

#### Laboratory data

Safety Laboratory parameters (blood chemistry hematology, coagulation and urinalysis) will be listed and abnormal parameters flagged as high (H) or low (L). Changes from baseline (continuous variables) will be summarized by each treatment dose based on scheduled values.

For summary statistics, the lab value with "<" will be replaced with numeric value by removing the "<" sign. In the listings the values will be displayed as originally reported by the laboratory.

Laboratory parameter values will be graded according to the National Cancer Institute Common Terminology Criteria for Adverse Events (CTCAE; v4.03, published June 14, 2010). Parameters, not present in the above referenced document will not be graded. Shift tables by treatment group will be produced for these laboratory parameters by grade. These tables will summarize the number of subjects with each baseline grade relative to the normal ranges and changes to the worst highest grade assessed post-dose during the study.

Individual profiles will be presented for the following laboratory parameters: GGT, ALT, AST, Hb, Creatinine, RBC, WBC, Potassium, Sodium, Uric Acid, Albumin, Total Protein and neutrophils.

#### ECG

The ECG parameters will be measured at the specified time-points, including heart rate, PR, RR, QRS, QT and QTcF intervals. For summary statistics the average of all time-point ECG readings will be calculated, as well as changes from pre-treatment baseline values will be assessed by each treatment dose.

An outlier analysis will be performed that will summarize the frequency and percentage of subjects who meet any of the following outlier criteria at each visit by treatment group as follows:

- QT, QTcF interval > 450 msec
- QT, QTcF interval > 480 msec
- QT, QTcF interval > 500 msec

C15045 (ALXN1210-HV\_104) SAP Final 2.0 - 09Oct2016.doc

Page 8 of 13

- QT, QTcF interval increases from baseline > 30 msec
- QT, QTcF interval increases from baseline > 60 msec

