Subjects in Cohorts 1 and 2 (Single Ascending Dose [SAD] Phase) will participate in the study for up to 27 or 30 weeks, respectively, including a screening period of up to 70 days, followed by a 120-day (Cohort 1) or 140-day (Cohort 2) dosing and observation period for safety, immunogenicity, PK, and PD assessments after study drug administration. Subjects in Cohort 3 (Multiple Set Dose [MSD] Phase) will participate in the study for approximately 52 weeks, including a screening period of up to 70 days, a treatment period of 112 days, and a 185-day observation period for safety, immunogenicity, PK, and PD assessments after the fifth dose of study drug. Subjects in Cohort 1 will utilize contraception for a minimum of 6 months after last dose, whereas subjects in Cohorts 2 and 3 will utilize contraception for a minimum of 8 months after last dose.

Number of subjects (planned):

Up to 16 subjects are planned for evaluation of the primary and secondary objectives, and a maximum of 22 subjects could be enrolled and dosed. See the synopsis section "Methodology" regarding addition of subjects who withdraw or are withdrawn from the study after dosing. The total number of subjects dosed (including potential added subjects) will remain within a maximum of 6 subjects each in Cohorts 1 and 2 and 10 subjects in Cohort 3, for a maximum of 22 subjects in this study.

Diagnosis and main criteria for inclusion:

All subjects must adhere to the following inclusion/exclusion criteria. Subjects who fail to meet eligibility criteria may not be rescreened for participation in the study unless the condition is transient, self-limited, and easily treatable, and is expected to be resolved at the time of dosing, as agreed by the investigator and medical monitor.

Inclusion:

- 1. Healthy Japanese males or females aged 25 through 55 years, inclusive (subjects must have lived outside of Japan for ≤ 10 years and be first generation Japanese, defined as born in Japan and having 4 biologic grandparents who are ethnic Japanese).
- 2. Body mass index (BMI) from 18 through 29.9 kg/m², inclusive, and weight between 50 and 100 kg, inclusive.
- 3. QT interval (corrected using the Fridericia's formula; QTcF) ≤ 450 msec for males and ≤ 470 msec for females at screening and prior to dosing on Day 1.
- 4. Willing and able to give written informed consent and comply with the study visit schedule.

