10. SELECTION AND WITHDRAWAL OF SUBJECTS

10.1. Subject Inclusion Criteria

Subjects must meet all of the following criteria in order to be eligible for the study:

- 1. Healthy Japanese males or females aged 25 through 55 years, inclusive (subjects must have lived outside of Japan for \leq 10 years and be first generation Japanese, defined as born in Japan and having 4 biologic grandparents who are ethnic Japanese).
- 2. Body mass index (BMI) from 18 through 29.9 kg/m², inclusive, and weight between 50 and 100 kg, inclusive.
- 3. QT interval (corrected using the Fridericia's formula; QTcF) \leq 450 msec for males and \leq 470 msec for females at screening and prior to dosing on Day 1.
- 4. Willing and able to give written informed consent and comply with the study visit schedule.
- 5. Documented vaccination with MCV4 at least 56 days and not more than 3 years prior to dosing. Documentation must include a positive SBA to confirm an immune response before study drug administration.
- 6. Vaccination with serogroup B meningococcal vaccine at least 56 days prior to dosing on Day 1, with a booster administered at least 28 days prior to dosing on Day 1, with at least 28 days between the first and second injections.
- 7. Female subjects of childbearing potential must use highly effective contraception as defined below, starting at screening and continuing until at least 6 months (Cohort 1) or 8 months (Cohorts 2 and 3) after the last dose of ALXN1210.

Highly effective contraceptive methods for females are as follows*:

- Combined (estrogen and progestogen containing) hormonal contraception associated with inhibition of ovulation:
 - Oral
 - Intravaginal
 - Transdermal
- Progestogen-only hormonal contraception associated with inhibition of ovulation:
 - Oral
 - Injectable
 - Implantable
- Intrauterine device
- Intrauterine hormone-releasing system
- Bilateral tubal occlusion

* It is recommended that heterosexually active female subjects of childbearing age who take oral contraceptives and penicillin V, or any other antibiotics with the potential to reduce the effectiveness of hormonal contraception, should use a barrier method (eg, condom or diaphragm and spermicide) in addition to the oral contraceptive medication.

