16.1.5. Electrocardiogram

A triplicate 12-lead ECG will be obtained after the subject has been resting for at least 5 minutes. The timing of ECGs is described in the Schedules of Assessments (Section 9). In addition, continuous cardiac registration will be performed at each dose administration from predose through the duration of infusion.

Heart rate, PR, QRS, RR, and QT will be measured and corrected QTcF intervals will be calculated.

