19.6. Safety Analysis

Safety analyses will be performed on the safety population, and will be reported by each treatment dose. Safety analyses will include an analysis of all AEs, ECGs, clinical laboratory data, physical examinations, and vital sign measurements and will be presented using descriptive statistics. No inferential statistical analyses are planned on the safety parameters of this study. The incidence of treatment-emergent AEs and SAEs will be summarized by system organ class and preferred term for each treatment dose and overall, by severity, and by relationship to study drug. Serious AEs and AEs resulting in withdrawal from the study will be listed. Subjects having multiple AEs within a category (eg, overall, system organ class, preferred term) will be counted once in that category. For severity tables, a subject's most severe event within a category will be counted.

Changes from baseline in vital signs and laboratory assessments (chemistry, CBC with differential, and urinalysis) will be summarized by each treatment dose. Laboratory parameter values will be graded according to the National Cancer Institute Common Terminology Criteria for Adverse Events (CTCAE; v4.03, published June 14, 2010). Shift tables by treatment group will be produced for these laboratory parameters. These tables will summarize the number of subjects with each baseline grade relative to the normal ranges and changes to the worst highest grade assessed postdose during the study.

The ECG parameters will be measured at the specified time points, including heart rate, PR, RR, QRS, QT, and corrected QTcF intervals. The average of the triplicate ECG readings at the time points collected will be calculated, and changes from pretreatment baseline values will be assessed by each treatment dose.

An outlier analysis will be performed that will summarize the frequency and percentage of subjects who meet any of the following outlier criteria at each visit by treatment group:

- OT, OTcF interval > 450 msec
- QT, QTcF interval > 480 msec
- QT, QTcF interval > 500 msec
- QT, QTcF interval increases from baseline > 30 msec
- QT, QTcF interval increases from baseline > 60 msec

All concomitant medications will be coded using the WHO Drug Dictionary, and the frequency and percentage of concomitant medications will be summarized.

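### The ECG outlier counts ignore the predose value and include uncorrected QT, so some subjects are flagged with no change, or from heart rate alone

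*SAP*

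**What the plan says.** SAP Section 4.4 (ECG) plans an outlier table giving the "frequency and percentage of subjects who meet any of the following outlier criteria at each visit", by treatment group. There are three absolute criteria, the lowest being "QT, QTcF interval > 450 msec", followed by >480 and >500 msec. There are two change criteria, "QT, QTcF interval increases from baseline > 30 msec" and the same with >60 msec. Protocol 19.6 carries the same five, so the two documents agree.

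Neither document splits the list by sex, makes an absolute criterion depend on the predose value, or says whether QT and QTcF go into separate rows.

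Other relevant places:
- **Eligibility.** Both sexes may enrol. Inclusion criterion 3 (Protocol synopsis and 10.1) limits QTcF to "≤ 450 msec for males and ≤ 470 msec for females at screening and prior to dosing on Day 1". The eligibility criteria set no limit on uncorrected QT and no numeric limit on heart rate.
- **Measurement.** Protocol 16.1.5: "Heart rate, PR, QRS, RR, and QT will be measured and corrected QTcF intervals will be calculated".
- **Baseline.** SAP Section 4 takes the last assessment before the first dose.
- **Design.** Every subject receives ALXN1210. Planned cohorts are 4, 4 and 6 to 8.

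**The concern.** An outlier table in a safety study should draw attention to values that may have arisen on treatment. Two features of this list let in values that did not.

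First, a subject already above an absolute threshold before dosing is counted at each later visit, exactly like a subject who crossed it after dosing. The eligibility rule makes this possible for women.

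Second, uncorrected QT varies with heart rate, which is the reason a corrected interval is calculated at all. Applying both the absolute and the change criteria to uncorrected QT means that a slower pulse can produce a flag while QTcF is constant.

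Change in ECG parameters is a listed safety endpoint, and safety is the primary objective. With no placebo group and very small cohorts, a reader has little within the table to set such a count against. For laboratory data the SAP does account for baseline status, through shift tables from baseline grade to worst post-dose grade. The ECG outlier table has no equivalent.

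**Working it through.** The documents give no expected rate for this table, so there is no stated figure to reproduce. The check compares the thresholds with the eligibility limits and then applies the Fridericia relation.

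**1. Who can be above a QTcF threshold before dosing?** Limits are from Inclusion criterion 3; thresholds are from SAP 4.4.

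| | Highest eligible predose QTcF | Can start >450? | Can start >480 or >500? |
|---|---|---|---|
| Men | 450 msec | No | No |
| Women | 470 msec | Yes, at 451 to 470 | No |

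Take a woman with predose QTcF of 455 msec who stays at 455. Her change is 455 − 455 = 0. She is counted in the >450 row at every visit and in neither change row.

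**2. Change in uncorrected QT from heart rate alone.** Fridericia: QTcF = QT / RR^(1/3), with RR = 60/HR in seconds. Hence QT = QTcF × (60/HR)^(1/3). The QTcF and heart-rate values below are illustrative; QTcF is held constant within each row.

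| QTcF (msec) | Heart rate (bpm) | QT (msec) | Change | Row met |
|---|---|---|---|---|
| 410 | 70 to 55 | 389.5 to 422.1 | +32.6 | >30 |
| 420 | 65 to 50 | 408.9 to 446.3 | +37.4 | >30 |
| 410 | 80 to 50 | 372.5 to 435.7 | +63.2 | >60 |

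**3. Absolute exceedance on uncorrected QT.** Solving QT > 450 gives HR < 60 × (QTcF/450)^3.

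| QTcF (msec) | QT exceeds 450 msec when heart rate is below |
|---|---|
| 410 | 45.4 bpm |
| 430 | 52.4 bpm |
| 450 (limit for men) | 60.0 bpm |
| 470 (limit for women) | 68.4 bpm |

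So eligible men as well as women can exceed 450 msec on uncorrected QT before any dose.

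**4. Weight of one subject.** 1/4 = 25%, 1/6 = 16.7%, 1/8 = 12.5%.

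**5. How often, per visit, with no drug effect?** The documents give no ECG distribution, so this is a simulation on assumed inputs: mean QTcF 395 to 415 msec in men and 405 to 425 in women, between-subject SD 15, within-subject SD 8, mean heart rate 55 to 65 bpm with SD about 8, truncated at the eligibility limits.

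| | Predose QTcF >450 | QTcF >450 at a given visit | QT >450 at a given visit |
|---|---|---|---|
| Men | 0% | 0.0% to 0.9% | 1.0% to 21.9% |
| Women | 0.4% to 6.5% | 0.4% to 6.5% | 2.3% to 34.0% |

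On QTcF the effect is small and falls mainly on women. On uncorrected QT it can be large and depends heavily on resting heart rate. For women, the predose and post-dose QTcF rates coincide when the drug does nothing. A baseline column would therefore give the table a background figure that it otherwise lacks.

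**The case against.** The case for leaving the list alone has real weight.

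- **Reach.** On QTcF the missing baseline condition affects only women at 451 to 470 msec. No eligible man starts above 450, and nobody eligible starts above 480 or 500. If 8 of the 16 planned subjects were women (an assumption), 0.4% to 6.5% of 8 is about 0.03 to 0.52 women in the whole study. This stands.
- **Consequence.** Safety analysis is descriptive. Escalation and stopping in Protocol 8.4 rest on graded drug-related adverse events, not on this table. This stands too.
- **A drug effect stays visible.** A reader might infer that a true signal could not be told from these flags. The documents do not support that. The QTcF rows for increases >30 and >60 msec are in the same list, and an unchanged woman at 455 meets neither. Changes from baseline in heart rate, RR and QTcF are also summarized.
- **QT and QTcF may be tabulated separately.** If so, the QTcF rows are untouched by heart rate. The text leaves this open, and the uncorrected-QT rows would still hold flags produced by pulse alone.
- **Predose visits may be shown.** Counting at each visit does not exclude screening or Day 1 predose. But separate visit counts do not show whether the same subject was above the threshold before and after dosing.

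A reader might also conclude that the lowest category should be 470 msec for women, to match eligibility. That is a trade-off, not a correction. A woman moving from 435 to 460 msec (+25) is flagged now and would then meet no criterion. Nothing in the documents says that descriptive categories must equal eligibility limits.

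Finally, the chance of at least one exceedance across many visits is higher: 7.0% to 19.8% of women over nine visits, with mean QTcF of 415 to 425 and the same SDs. That does not describe this table, which counts each visit separately.

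**Conclusion.** The point holds within limits. As written, the absolute counts do not separate a value present before dosing from one that appeared afterwards, and the uncorrected-QT counts can arise from heart rate alone. The first follows from comparing Inclusion criterion 3 with the outlier list and needs no assumption. The second is arithmetic on the Fridericia formula. Only the frequencies rest on assumed means and SDs.

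It does not follow that women or subjects with slow heart rates are flagged in general. The flags reach women with predose QTcF of 451 to 470 msec, and subjects whose QTcF and heart rate together carry uncorrected QT past a threshold.

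The effect is confined to how descriptive percentages read. In an uncontrolled study, one subject who contributes 25%, 16.7% or 12.5% of a cohort is enough to make a clearer table worthwhile. It is an inexpensive improvement, not a threat to the study's conclusions.

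**What to change.** In SAP Section 4.4 (ECG):

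1. Keep the >450, >480 and >500 msec categories for both sexes.
2. Count a post-dose exceedance as new only when the subject's baseline value was at or below that threshold. Show baseline exceedances in a separate column.
3. Separate QTcF from uncorrected QT. Base the outlier counts, absolute and change, on QTcF, and present uncorrected QT in listings only.

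With these changes the woman unchanged at 455 msec moves to the baseline column, the woman going from 435 to 460 is still flagged, and constant QTcF with a slower pulse produces no count. A woman just below 450 at baseline can still cross it through visit-to-visit variation, which the change rows help to interpret.

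Protocol 19.6 has the same list, so the SAP should state that this refines it. The cost is SAP wording and one table shell. No new data are needed.

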#### **Previous and concomitant medications**

All previous and concomitant medications will be coded using the World Health Organization (WHO) Drug Dictionary version June 1, 2015 and the frequency and percentage of concomitant medications will be summarized by Anatomical Therapeutic Chemical (ATC) and Preferred name.

#### Physical examination

Physical examination data will be listed. Change from baseline to each visit will be presented for each item of the Physical Examination separately, using shift tables.

#### Infusion site evaluation

Data from the Infusion site evaluations will be listed individually.

#### Visual assessment scale for pain at infusion site

Data from the Pain at infusion site will be listed.

#### 4.5 Pharmacokinetic Analysis

All serum concentration data will be listed for each individual subject and summarized at each time point by treatment group using the following descriptive statistics.

- N (the number of subjects)
- Arithmetic mean
- SD
- Arithmetic CV (inter-subject coefficients of variation)
- Geometric mean
- Geometric CV (inter-subject coefficients of variation)
- Median
- Minimum
- Maximum.

When a Below the Level of Quantification (BLQ) value occurs in a profile before the first measurable concentration, it is assigned a value of zero concentration. When a BLQ value occurs after a measurable concentration in a profile and is followed by a value above the Lower Level of Quantification (LLQ), then the BLQ will be omitted following visual inspection of the serum concentration versus time profile to assess the appropriateness of this assignment. When a BLQ value occurs at the end of a collection profile (after the last quantifiable concentration), the value is treated as missing data. When two BLQ values occur in succession, the profile is deemed to have terminated at the first BLQ value and any subsequent concentrations are omitted from PK calculations.

Samples with no reportable value due to a bioanalytical issue or missing samples should be set to missing, and will not be included in the PK calculations.

When calculating the mean or median value for a concentration at a given time point, all BLQ values will be set to zero except when an individual BLQ falls between two quantifiable values, in which case it will be omitted.

For tabulation, graphical representation and calculation purposes, all samples with no reportable value (or missing samples) observed after dosing will be set to missing.

The figures of individual and mean concentrations versus nominal time on linear and semi-log scale will be plotted.

The individual serum concentration data for ALXN1210-treated subjects, with actual sampling dates and times calculated relative to the start of the infusion, will be used to derive the PK parameters by non-compartmental analyses using Phoenix WinNonlin 6.3 or higher.

The following PK parameters will be estimated:

- Observed maximum serum concentration following all ALXN1210 doses (Cmax) following single dose (Cohort 1 and 2) and doses 1 and 5 (Cohort 3);
- Dose-normalized  $C_{max}$ , following single dose (Cohort 1 and 2) and doses 1 and 5 (Cohort 3);
- Time to maximum observed serum concentration (tmax) following single dose (Cohort 1 and 2) and doses 1 and 5 (Cohort 3);
- Trough serum concentrations (Ctrough) just prior to Doses 2 to 5, and 28 days after the 5th dose (Cohort 3);
- Area under the serum concentration versus time curve from time 0 to the last quantifiable concentration (AUCt) after single dose (Cohort 1 and 2) and after dose 5 (Cohort 3);
- Dose-normalized AUCt after single dose (Cohort 1 and 2) and following dose 5 (Cohort 3);
- AUC from time 0 (dosing) to the end of the dosing interval (AUCτ) following doses 1 and 5 (Cohort 3). Following Dose 5, calculated over dosing interval (28 days);
- Terminal-phase elimination rate constant ( $\lambda_z$ ) after single dose (Cohort 1 and 2) and after dose 5 (Cohort 3);
- Terminal elimination half-life (t/2) after single dose (Cohort 1 and 2) and after dose 5 (Cohort 3);
- Total body clearance of drug from the serum (CL) after single dose (Cohort 1 and 2) and after dose 5 (Cohort 3);
- Volume of distribution at steady state (Vss) (Cohort 3);
- Assessment of steady state (Cohort 3);
- Accumulation at steady state (R) after the fifth dose (Cohort 3).

All pharmacokinetic parameters will be listed for each individual subject and summarized by treatment group using the following descriptive statistics.

- N (the number of subjects)
- Arithmetic mean
- SD
- CV
- Geometric mean
- Geometric CV

C15045 (ALXN1210-HV\_104) SAP Final 2.0 - 09Oct2016.doc

Page 10 of 13

- Median
- Minimum
- Maximum

Some PK parameters may not be calculated for all or some subjects if the concentration data are not deemed to be amenable to evaluation. Explanations for PK parameters that could not be estimated may be provided in the Clinical Study Report (CSR).

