7.2. Pharmacokinetic Endpoints

The following PK parameters will be evaluated:

- C_{max}
- Time to maximum observed serum concentration (t_{max})
- Observed minimum serum concentrations (C_{min}) just prior to Doses 2 to 5, and 28 days after the 5th dose
- Area under the serum concentration versus time curve from time 0 to the last quantifiable concentration (AUC_t) after each dose
- AUC from time 0 (dosing) to the end of the dosing interval (AUC_{τ})
- Apparent terminal-phase elimination rate constant (λ_z)
- t_½
- Total body clearance of drug from the serum (CL)
- Volume of distribution at steady state (V_{ss})
- Assessment of steady state
- Accumulation at steady state

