8. INVESTIGATIONAL PLAN

8.1. Overall Study Design

This is a Phase 1, open-label, single ascending and multiple set dose study designed to evaluate the safety, tolerability, immunogenicity, PK, and PD of ALXN1210 in healthy Japanese subjects.

All subjects are to be screened for eligibility in the study after providing written informed consent to participate. Subjects who fail to meet eligibility criteria may not be rescreened for participation in the study, unless the condition that led to eligibility failure is transient, self-limited, and easily treatable, and is expected to be resolved at the time of dosing, as agreed by the investigator and medical monitor.

A total of 3 cohorts and up to 16 subjects are planned for evaluation. The cohorts will be enrolled sequentially and all subjects will receive IV ALXN1210:

[figure not shown]
- Cohort 1, 400 mg single dose (N = 4)
- Cohort 2, 800 mg single dose (N = 4)
- Cohort 3, 800 mg Q4W for a total of 5 doses (N = 6 to 8)

A Safety Review Committee (SRC) will conduct a review of the available clinical and safety data after the last subject in the 400 mg cohort (Cohort 1) has completed Day 15 to determine if dose escalation to 800 mg may proceed (Cohort 2). The SRC will conduct a review of all available clinical and safety data after the last subject in the 800 mg cohort (Cohort 2) has completed Day 15 to determine if dosing in Cohort 3 may begin. Dose escalation to the multiple repeated dose phase will proceed as scheduled and the study will continue as long as no prespecified toxicity events occur (see Table 3). Dose continuation within Cohort 3 after Period 2 will proceed following review of the available safety and tolerability data by the PI in accordance with the protocol's toxicity rules. Minimum data requirements do not apply for the PI review; however, it is expected to include available data up to 14 days after each dose.

Up to 2 subjects per cohort may be added if 2 or more subjects discontinue before Day 15 (first dose only for Cohort 3) for reasons other than drug-related AEs, and after consultation with the SRC. All enrolled subjects will be included in analyses as appropriate. Subjects who have been dosed and who withdraw from the study will be followed for safety assessments through the last study visit, if possible.

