8.2. Number of Subjects

Up to 16 subjects are planned for evaluation of the primary and secondary objectives, and a maximum of 22 subjects could be enrolled and dosed. See the synopsis section "Methodology" regarding addition of subjects who withdraw or are withdrawn from the study after dosing. The total number of subjects dosed (including potential added subjects) will remain within a maximum of 6 subjects each in Cohorts 1 and 2 and 10 subjects in Cohort 3, for a maximum of 22 subjects in this study.

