### 4.6 Dose Proportionality

Dose proportionality of the 400mg and 800mg ALXN1210 doses may be assessed for the following PK parameters:

- dose-normalized AUCt
- dose-normalized Cmax (Cohort 1, 2 and Cohort 3 after first dose)

The parameters will be analyzed using the power model [1], where the ratio of geometric means and the corresponding 90% confidence interval will be derived. Dose proportionality will be concluded if the 90% confidence interval of the ratio contains 1.

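### The first 800 mg dose is summarised by one AUC measure in Cohort 2 and another in Cohort 3, so first-dose AUC cannot be pooled across them, nor Cohort 3 compared with 400 mg

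*SAP*

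**What the plan says.** Protocol 8.1 plans "Cohort 2, 800 mg single dose (N = 4") and "Cohort 3, 800 mg Q4W for a total of 5 doses (N = 6 to 8"). With added subjects, Protocol 8.2 allows a "maximum of 6 subjects each in Cohorts 1 and 2 and 10 subjects in Cohort 3". Protocol Tables 12 and 13 give both 800 mg cohorts the same volume (160 mL), rate (686 mg/h) and approximate duration (90 minutes).

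SAP 2.2 and 4.5 assign the AUC parameters as follows:
- AUCτ is derived "following doses 1 and 5 (Cohort 3). Following Dose 5, calculated over dosing interval (28 days"). It is not listed for Cohorts 1 and 2.
- AUCt is derived "after single dose (Cohort 1 and 2) and after dose 5 (Cohort 3"). It is not listed for Cohort 3 after Dose 1.

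SAP 4.6 says that dose proportionality of 400 mg and 800 mg may be assessed on two parameters. For dose-normalised Cmax it names the data: "Cohort 1, 2 and Cohort 3 after first dose". For AUC it lists only dose-normalised AUCt, with no cohort or dose named.

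Protocol 7.2 is wider than the SAP. It lists "Area under the serum concentration versus time curve from time 0 to the last quantifiable concentration" after each dose, and it does not confine AUCτ to Cohort 3. Protocol 19.7 does the same.

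**The concern.** Characterising single-dose PK is a secondary objective, and Protocol 8.3 intends the PK data for bridging to non-Japanese studies. Ten to twelve subjects are planned to receive a first 800 mg dose under the same nominal conditions. The SAP splits them between two AUC measures that cover different time spans, so the values cannot be combined. The 400 mg cohort has only AUCt, so the 6 to 8 first-dose AUC values from Cohort 3 cannot enter the 800 versus 400 mg comparison. That comparison rests on 4 against 4 for AUC, although SAP 4.6 accepts the Cohort 3 first dose as comparable for Cmax.

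What is at stake is the precision of one first-dose exposure measure and of an optional dose comparison. The primary objective, safety, is not affected.

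**Working it through.** **1. Are the first-dose data comparable?** Nominal PK times, from Protocol Table 14:

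| | Cohort 2 | Cohort 3, Dose 1 |
|---|---|---|
| Dosing day | predose, EOI, EOI + 30 min, 4 h, 8 h | same |
| Later | 24, 48, 96, 168, 336, 504 h | same |
| 672 h | Day 29 sample | Day 29 sample before Dose 2 |

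All 12 points match. Cohort 1 has the same points.

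**2. Would AUCt after Dose 1 in Cohort 3 be enough?** No. It would end at Day 29, while Cohort 2 is sampled to Day 140. Take a mono-exponential decline and the half-life range of 30.8 to 32.4 days in Protocol 8.3. The fraction of total AUC by day d is 1 − 2^(−d/half-life).
- d = 28: 1 − 2^(−28/30.8) = 0.467 and 1 − 2^(−28/32.4) = 0.451, so about 45% to 47%.
- d = 139 (Day 140): 0.956 and 0.949, so about 95% to 96%.

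AUCt after Dose 5 does not help either, because it includes drug accumulated from earlier doses. A fixed 0 to 28 day window is like for like.

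**3. Gain for the 800 mg mean.** Combined n = 4 + 6 = 10 to 4 + 8 = 12. The standard error of the log-mean is SD/√n, so the reduction against n = 4 does not depend on the SD:
- n = 10: 1 − √(4/10) = 0.37
- n = 12: 1 − √(4/12) = 0.42

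**4. Gain for the 800/400 mg ratio.** With two dose levels the power model reduces to a two-group comparison of log values. The 90% half-width on the log scale is t(0.95, 4 + n − 2) × SD × √(1/4 + 1/n), where n is the number of subjects at 800 mg and the 400 mg cohort has 4. The documents give no between-subject SD for AUC(0-28 d). Assume 0.19, which SAP 4.2 gives as a within-subject SD of log AUC∞:

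| 400 mg v 800 mg | t | SE | Half-width | 90% CI at ratio 1 |
|---|---|---|---|---|
| 4 v 4 | 1.943 | 0.1344 | 0.261 | 0.77-1.30 |
| 4 v 10 | 1.782 | 0.1124 | 0.200 | 0.82-1.22 |
| 4 v 12 | 1.761 | 0.1097 | 0.193 | 0.82-1.21 |

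The half-width falls by 1 − 0.200/0.261 = 23% to 1 − 0.193/0.261 = 26%, and this percentage holds for any common SD. The intervals themselves depend on it:
- SD 0.15: 0.81-1.23 (4 v 4), 0.85-1.17 (4 v 10), 0.86-1.16 (4 v 12).
- SD 0.30: 0.66-1.51, 0.73-1.37, 0.74-1.36.

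**5. The plan's own precision table.** SAP Table 1 prints 33.6%, 23.3% and 18.9% for n = 4, 6 and 8. Taking the stated definition literally, imprecision is 1 − exp(−t(0.95, n−1) × 0.19 × √(χ²(0.80, n−1)/(n−1))/√n), which gives 24.3%, 17.2% and 14.0%. Multiplying 0.19 by √2 gives 32.5%, 23.4% and 19.2%, close to the printed values, but the documents do not mention that factor. The table concerns AUC∞ and is not used in steps 1 to 4.

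**The case against.** Much of the case on the other side is right, and it limits the point.

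- **The Cohort 3 first-dose data are used.** A reader might infer that these profiles go to waste or are never combined with Cohort 2. The SAP does not support that. It plans Cmax, dose-normalised Cmax, tmax and AUCτ after Dose 1 and the trough before Dose 2, summarises all concentrations, and brings the Cohort 3 first dose into the Cmax comparison.
- **The sample-size target is not shown to be missed.** It is tempting to note that "it is preferred to estimate the PK parameters with a maximum imprecision of < 25"%, set this against the printed 33.6% for 4 subjects, and project a fall to about half. Those figures are for AUC∞, and the sized claim is for six subjects in Cohort 3. The definition as written gives 24.3% at n = 4, inside the target.
- **Other single-dose parameters gain nothing.** AUCt, clearance and half-life after a single 800 mg dose stay at 4 planned subjects.
- **No firm decision depends on it.** Dose proportionality is optional, and the 400 mg cohort stays at 4. The SAP concludes proportionality if the interval contains 1, and a narrower interval does not in itself make that rule more reliable. The missing AUC could be derived later and reported as a deviation.
- **Matching is confirmed for nominal times only.** Sampling windows are in a manual not provided, and Protocol 13.1 lets PK timing change after initial results.

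One defence fails. SAP 4 summarises by dose cohort and SAP 5 presents data by dose level, but neither creates a common AUC measure. The protocol's AUCt after each dose would not do so either, because of the different time spans in step 2.

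**Conclusion.** The point holds as a gap in parameter definition. The same first 800 mg dose is described by AUCt in 4 subjects and by a 28-day AUC in 6 to 8 others, and only the former has a 400 mg counterpart. Closing the gap lowers the standard error of the first-dose 800 mg log-mean for AUC(0-28 d) by 37% to 42% against Cohort 2 alone. It narrows the 800/400 mg interval by 23% to 26% on the log scale. Both percentages rest on planned numbers and a common SD. The interval limits also rest on the assumed between-subject log-SD.

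This is an inexpensive improvement to a secondary PK analysis that the sponsor should make. It is not a flaw that threatens the trial's conclusions.

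**What to change.** Before database lock, amend the SAP as follows:

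1. In 2.2 and 4.5, add AUC(0-28 d) and its dose-normalised form after the single dose in Cohorts 1 and 2. Name the Cohort 3 Dose 1 AUCτ as the same quantity. State how the 672 h endpoint is handled when the actual sampling time differs.
2. Report first-dose 800 mg Cmax and AUC(0-28 d) for Cohort 2 and Cohort 3 Dose 1 combined (10 to 12 planned subjects), beside the by-cohort results so that any difference between the sequentially enrolled cohorts is visible.
3. In 4.6, add dose-normalised AUC(0-28 d) for Cohorts 1, 2 and Cohort 3 after the first dose. Keep AUCt and state that it comes from Cohorts 1 and 2.
4. Note in the SAP that it narrows the protocol's AUCt after each dose, and why.

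The cost is one more noncompartmental parameter, its table rows and the wording, with no new samples, visits or subjects. The drawback is that AUC(0-28 d) covers less than half of total exposure, so the report should present it as a supplement to AUCt.
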